### Anticipated precision of rates and proportions, in general

The figure below illustrates precision for rates and proportions corresponding to binary outcomes indicating, for example, presence or change of a side-effect, perfect medication adherence, and resolution of a symptom. The analyses will provide statistical estimates of the population proportion ( $P$ ). The anticipated level of precision for the estimated proportion can be obtained from the figure. For example, hypothetically if  $N=100$  and  $P=0.50$  is the observed rate of perfect compliance for a treatment regimen, then half the width of a symmetric 95% confidence interval is  $W = 0.10$  and thus the approximate 95% confidence interval would be  $0.50 \pm 0.10$  or “[0.40, 0.60]. Larger sample sizes yield narrower confidence intervals.

Sample Size (N)

## 16 STUDY CONDUCT

### 16.1 Ethics

This study will be conducted in accordance with Good Clinical Practice (GCP), as defined by the International Conference on Harmonization (ICH) and in accordance with the ethical principles underlying European Union Directive 2001/20/EC and the United States Code of Federal Regulations, Title 21, Part 50 (21CFR50).

The study will be conducted in compliance with this protocol. The protocol and any amendments and the subject informed consent will receive Institutional Review Board (IRB) approval prior to initiation of the study.

All potential protocol deviations should be reported to UNC. Any serious breach to the protocol or principles of GCP in connection with the study or the protocol, which are likely to affect the physical or mental safety of study participants or the integrity of the study should be reported to UNC.

Personnel involved in conducting this study will be qualified by education, training, and experience to perform their respective tasks.

### 16.2 Responsibilities within the Study

The study shall be conducted as described in this approved protocol. Investigators should not implement any deviation or change to the protocol without prior discussion with UNC.

### **16.3 Reports and Publications**

The confidentiality of records that could identify participants within the database must be protected, respecting the privacy and confidentiality rules in accordance with the applicable regulatory requirement(s). The data collected during this study are confidential and proprietary to UNC. Any publications or abstracts arising from the PROP UP study require approval by UNC, the study sponsor, prior to submission of a publication or presentation. Investigators who wish to use PROP UP data for secondary analyses should present initial concept sheet to Steering Committee. Steering Committee will require 2 weeks to review abstracts prior to submission to scientific conferences and 1 month to review manuscripts prior to submission to a peer-reviewed journal.

### **16.4 Database Retention and Archiving**

Location of database and supporting documentation will be outlined in the final progress report submitted to PCORI.

The site investigators must retain all study records and source documents for at least 5 years after study completion (2023). Site investigators must contact UNC investigators prior to destroying any records associated with the PROP UP study.

## **17 DATA SAFETY MONITORING BOARD (DSMB)**

There are minimal physical or other safety concerns associated with an observational study in which patients complete surveys. Because this study poses minimal harm and safety issues to study participants, no DSMB was established.

## **18 DATA AND STUDY MONITORING PLAN (DSMP)**

The UNC investigators and DCC will meet weekly to review and monitor all aspects of the study: site recruitment, data completeness, data quality, protocol deviations, and any reported study-related adverse events. Regular reports will be prepared by the DCC to share with collaborating sites. Tables will show study progress by each clinical center and overall, including numbers consented, enrolled, data collected at each time point, study-related adverse events, and descriptive characteristics of the study sample.

PROP UP will utilize the secure REDCap data capture application hosted by UNC and the database will be monitored, maintained, and secured by REDCap data analysts of the DCC. REDCap has been used in over 15,360 projects with over 23,000 end users across 6 continents. REDCap is designed for interactive web-based data entry with real-time field validation. The DCC will also be responsible for database integrity checks, security (individual user logins, permissions based on need, and encrypted data transmission), and data retrieval and export. The secure server environment housing the database hardware is located within a hardened data center on the UNC campus, and is governed by standard University and School of Medicine information security guidelines. Weekly vulnerability detection scans, are performed by a third party vendor, which include full administrative credentials to perform maximum detection techniques. Real-time virus protection software is implemented, and weekly full system virus scans are performed.

## **19 PATIENT SAFETY AND MONITORING PLAN (PSMP)**

### **19.1 Standard Medical Care**

Site clinical hepatology teams are expected to oversee the health needs and medical treatment of patients who are enrolled in this observational study. Prior to enrolling in this study, participants will have been medically

cleared for HCV treatment by a site hepatology provider. Once HCV therapy commences, patients are managed by the site clinical team according to site standard clinical practices.

## **19.2 Risks of Study Participation**

The psychological risks directly posed by an observational study and survey completion are judged to be minimal and rare (<1%). Patients could experience mild embarrassment when responding to questions if posed by research staff. To reduce this risk and prepare patients, the RC will remind study participants that participation is completely voluntary and that they do not have to answer questions that make them uncomfortable. RCs will also remind participants of all study procedures in place to protect the confidentiality of their data. RCs will be trained to collect PRO data in a professional, objective, nonjudgmental and supportive manner.

The risk of breach of confidentiality of patient information is judged to be minimal and rare (<1%). This risk, and all procedures to prevent it, should be discussed by the RC during the consenting process. RC will remind patients of safeguards to protect personal information and breach of confidentiality including use of private rooms, storage of hard copy documents in locked offices and/or cabinets, compliance with site information technology security recommendations, and use of a secure, encrypted database.

The social risks are judged to be minimal and rare (<1%) but could include loss of reputation or social stigma if participation in this study leads others to become aware of a patient's medical condition. The RC will discuss this risk and encourage patients to consider risk prevention, especially as related to communication with research staff via email and phone interviews.

## **19.3 Handling of Non-Study Related Harms or Adverse Events**

[figure not shown]
Treatment for HCV may cause side effects and adverse events related to pre-existing conditions and advanced liver disease. These harms are not considered related to study participation and are expected to be handled and managed by the site clinical providers per site standard clinical protocols for handling medical or psychiatric concerns. Non-study related harms or adverse events will not be reportable to UNC, the UNC IRB, or the sponsor.

The site research team or the UNC Call Center may become aware of a patient's medical or psychiatric concern through in-person or phone contact. The research staff will explain to the patient that research is a separate activity from clinical care and will encourage the patient to notify the clinical hepatology team at their center. In the event that a patient expresses an urgent matter or a crisis (e.g., suicidality, homicidality), the research team will be trained to use good clinical judgement and standard operating procedures (e.g., refer to liver provider, go to closest emergency room). RCs should review site standard operating procedures for handling medical and psychiatric crises.

## **19.4 Handling of Study-related harms or unanticipated adverse events**

Harms or adverse events related to study participation in this observational survey study are expected to be extremely rare. Nonetheless, should an unanticipated study-related harm occur at a site that is judged by the site PI to be partially or fully related to study participation, the site will report this study harm to their own IRB if indicated by the site IRB standard operating procedures. Unanticipated study-related adverse events may be physical, psychological, social, or legal in nature. The site must notify UNC of the event within 10 days for study purposes. UNC will not report these events to the UNC IRB, since sites are under the jurisdiction of their own IRBs. However, overall study-related harms or unanticipated adverse events will be tracked by UNC and included in six-month progress reports to PCORI. The UNC investigators will discuss any study-related adverse events that are reported and the DCC will maintain a cumulative summary table of events, by site and date reported.

## 20 PROP UP RESEARCH TEAM

## GLOSSARY OF TERMS AND ABBREVIATIONS

Adverse event (AE)

Agency for Health Research and Quality (AHRQ)

Center for Gastrointestinal Biology and Disease Center (CGIBD)

Clinically Important Difference (CID)

Comparative Effectiveness Research (CER)

Confidence Intervals (CI)

Consolidated Standards of Reporting (CONSORT)

Data Coordinating Center (DCC)

Data Safety Monitoring Board (DSMB)

Data and Safety Monitoring Plan (DSMP)

Doubly Robust (DR)

Food and Drug Administration (FDA)

Good Clinical Practice (GCP)

Headache Impact Test (HIT)

Health Insurance Portability and Accountability Act (HIPAA)

Health-related Quality of Life (HRQOL)

Hepatitis C Virus (HCV)

Heterogeneity of Treatment Effect (HTE)

Human Immunodeficiency Virus (HIV)

International Conference on Harmonisation (ICH)

Interferon (IFN)

Institutional Review Board (IRB)

Instrumental Variable (IV)

Inverse-probability Weighted (IPW)

Information Technology Services (ITS)

Memorial Symptom Assessment Scale (MSAS)

Patient-centered Outcomes Research (PCOR)

The Patient Centered Outcomes Research Institute (PCORI)

Patient Engagement Group (PEG)

Principal Investigator (PI)

Patient Reported Outcome (PRO)

Patient-Reported Outcomes Measurement Information System (PROMIS)

Patient-Reported Outcomes Project of HCV-TARGET (PROP-UP)

Research Electronic Data Capture system (REDCap)

Research Coordinator (RC)

Sofosbuvir (SOF)

Standard Deviation (SD)

Standard Operating Procedures (SOP)

Sustained Virological Response (SVR)

Total Memorial Symptom Assessment Scale (TMSAS)

Voils Medication Adherence Survey (VMAS)

### 1. Anticipated Sample Sizes that May be Observed

#### Anticipated Sample Sizes that May be Observed

	Treatment Regimen	Cirrhotic	non-Cirrhotic	Combined
Genotype 1	Harvoni	480	480	960
	Zepatier	80	80	160
	Viekira Pak	40	40	80
Genotype 2 & 3	daclatasvir/sofosbuvir	40	40	80
	sofosbuvir/velpatasvir**	60	60	120
	Combined	800	800	1600

Note: \* Potential subsamples within treatment regimens may include patients with and without cirrhosis or patients with and without a mental health or substance abuse history. \*\* SOF/VEL is pan-genotypic and may also be used with genotype 1 patients. Anticipated FDA approval: June 28, 2016

## 2. Tabular Summary of Performance Curve Figures

PRO\_measure = MSAS with Conjectures = { SD = 0.6 [0.45, 0.75] and serial correlation is R = 0.50 }

a difference of 0.10 points on the MSAS scale will be considered clinically important

Figure	MS	Groups	N	procedure	X_80	X_90
1-1	1, 3, 4	1	1500	Confidence interval [1]	0.03 [0.02,0.04]	0.03 [0.02,0.04]
1-2	1, 3, 4	1	960	Confidence interval [1]	0.04 [0.03,0.05]	0.04 [0.03,0.05]
1-3	1, 3, 4	1	160	Confidence interval [1]	0.10 [0.07,0.12]	0.10 [0.08,0.13]
1-4	1, 3, 4	1	120	Confidence interval [1]	0.11 [0.09,0.14]	0.12 [0.09,0.15]
1-5	1, 3, 4	1	100	Confidence interval [1]	0.13 [0.09,0.16]	0.13 [0.10,0.16]
1-6	1, 3, 4	1	80	Confidence interval [1]	0.14 [0.11,0.18]	0.15 [0.11,0.18]
1-7	1, 3, 4	1	1500	test Ho: 'mean change is zero' [2]	0.04 [0.03,0.05]	0.05 [0.04,0.06]
1-8	1, 3, 4	1	960	test Ho: 'mean change is zero' [2]	0.05 [0.04,0.07]	0.06 [0.05,0.08]
1-9	1, 3, 4	1	160	test Ho: 'mean change is zero' [2]	0.13 [0.10,0.17]	0.15 [0.12,0.19]
1-10	1, 3, 4	1	120	test Ho: 'mean change is zero' [2]	0.15 [0.12,0.19]	0.18 [0.13,0.22]
1-11	1, 3, 4	1	100	test Ho: 'mean change is zero' [2]	0.17 [0.13,0.21]	0.20 [0.15,0.25]
1-12	1, 3, 4	1	80	test Ho: 'mean change is zero' [2]	0.19 [0.14,0.24]	0.22 [0.17,0.28]
1-13	1, 3A, 4	2	800 + 800	test Ho: 'mean diff. is zero' [3]	0.08 [0.06,0.11]	0.10 [0.07,0.12]
1-14	1, 3A, 4	2	1500 + 100	test Ho: 'mean diff. is zero' [3]	0.18 [0.13,0.22]	0.20 [0.15,0.25]
1-15	1, 3A, 4	2	400 + 400	test Ho: 'mean diff. is zero' [3]	0.12 [0.09,0.15]	0.14 [0.10,0.17]
1-16	1, 3A, 4	2	160 + 120	test Ho: 'mean diff. is zero' [3]	0.20 [0.15,0.25]	0.24 [0.18,0.29]
1-17	1, 3A, 4	2	160 + 80	test Ho: 'mean diff. is zero' [3]	0.23 [0.17,0.29]	0.27 [0.20,0.33]
1-18	1, 3A, 4	2	80 + 80	test Ho: 'mean diff. is zero' [3]	0.27 [0.20,0.33]	0.31 [0.23,0.39]
1-19	1, 3A, 4	2	960 + 80	test Ho: 'mean diff. is zero' [3]	0.20 [0.15,0.25]	0.23 [0.17,0.29]
1-20	1, 3A, 4	2	960 + 160	test Ho: 'mean diff. is zero' [3]	0.14 [0.11,0.18]	0.17 [0.13,0.21]

[1]  $\Pr[\text{Confidence Interval's half-width will be } < X_{80}] = 0.80$

[2]  $\Pr[p < \alpha | \text{population mean change} = X_{80}] = 0.80$

[3]  $\Pr[p < \alpha | \text{population mean difference} = X_{80}] = 0.80$

[4]  $\Pr[p < \alpha | \text{population rate change} = X_{80}] = 0.80$

[5]  $\Pr[p < \alpha | \text{population rate difference} = X_{80}] = 0.80$

**PRO\_measure = PROMIS      with Conjectures = { SD = 10 [6, 12] and serial correlation is R = 0.50 }**

**a difference of 3 points on a PROMIS scale will be considered clinically important**

Figure	MS	Groups	N	procedure	X_80	X_90
2-1	1, 3, 4	1	1500	Confidence interval [1]	0.52 [0.31,0.62]	0.52 [0.31,0.63]
2-2	1, 3, 4	1	960	Confidence interval [1]	0.65 [0.40,0.78]	0.66 [0.41,0.79]
2-3	1, 3, 4	1	160	Confidence interval [1]	1.63 [0.98,1.96]	1.67 [1.01,2.01]
2-4	1, 3, 4	1	120	Confidence interval [1]	1.90 [1.14,2.29]	1.96 [1.18,2.35]
2-5	1, 3, 4	1	100	Confidence interval [1]	2.10 [1.26,2.52]	2.16 [1.30,2.60]
2-6	1, 3, 4	1	80	Confidence interval [1]	2.37 [1.42,2.84]	2.45 [1.47,2.94]
2-7	1, 3, 4	1	1500	test Ho: 'mean change is zero' [2]	0.72 [0.44,0.87]	0.84 [0.50,1.01]
2-8	1, 3, 4	1	960	test Ho: 'mean change is zero' [2]	0.91 [0.54,1.09]	1.05 [0.63,1.26]
2-9	1, 3, 4	1	160	test Ho: 'mean change is zero' [2]	2.23 [1.34,2.67]	2.58 [1.55,3.09]
2-10	1, 3, 4	1	120	test Ho: 'mean change is zero' [2]	2.58 [1.55,3.09]	2.98 [1.79,3.58]
2-11	1, 3, 4	1	100	test Ho: 'mean change is zero' [2]	2.83 [1.70,3.39]	3.27 [1.96,3.93]
2-12	1, 3, 4	1	80	test Ho: 'mean change is zero' [2]	3.17 [1.90,3.81]	3.67 [2.20,4.40]
2-13	1, 3A, 4	2	800 + 800	test Ho: 'mean diff. is zero' [3]	1.40 [0.84,1.68]	1.62 [0.97,1.95]
2-14	1, 3A, 4	2	1500 + 100	test Ho: 'mean diff. is zero' [3]	2.92 [1.75,3.50]	3.38 [2.03,4.05]
2-15	1, 3A, 4	2	400 + 400	test Ho: 'mean diff. is zero' [3]	1.98 [1.19,2.38]	2.29 [1.38,2.75]
2-16	1, 3A, 4	2	160 + 120	test Ho: 'mean diff. is zero' [3]	3.40 [2.04,4.08]	3.93 [2.36,4.72]
2-17	1, 3A, 4	2	160 + 80	test Ho: 'mean diff. is zero' [3]	3.86 [2.32,4.63]	4.47 [2.68,5.36]
2-18	1, 3A, 4	2	80 + 80	test Ho: 'mean diff. is zero' [3]	4.46 [2.67,5.35]	5.16 [3.09,6.19]
2-19	1, 3A, 4	2	960 + 80	test Ho: 'mean diff. is zero' [3]	3.29 [1.98,3.95]	3.81 [2.29,4.57]
2-20	1, 3A, 4	2	960 + 160	test Ho: 'mean diff. is zero' [3]	2.40 [1.44,2.88]	2.78 [1.67,3.34]

[1]  $\Pr[\text{Confidence Interval's half-width will be } < X_{80}] = 0.80$

[2]  $\Pr[p < \alpha | \text{population mean change} = X_{80}] = 0.80$

[3]  $\Pr[p < \alpha | \text{population mean difference} = X_{80}] = 0.80$

[4]  $\Pr[p < \alpha | \text{population rate change} = X_{80}] = 0.80$

[5]  $\Pr[p < \alpha | \text{population rate difference} = X_{80}] = 0.80$

**PRO\_measure = HCV-PRO with Conjectures = { SD = 25.92 [23.641, 28.835] and serial correlation is R = 0.50 }**

**a difference of 10 points on the HCV-PRO scale will be considered clinically important**

Figure	MS	Groups	N	procedure	X_80	X_90
3-1	1, 3, 4	1	1500	Confidence interval [1]	1.34 [1.24,1.50]	1.35 [1.26,1.51]
3-2	1, 3, 4	1	960	Confidence interval [1]	1.67 [1.54,1.88]	1.71 [1.57,1.90]
3-3	1, 3, 4	1	160	Confidence interval [1]	4.23 [3.86,4.71]	4.34 [3.96,4.83]
3-4	1, 3, 4	1	120	Confidence interval [1]	4.94 [4.50,5.49]	5.07 [4.63,5.64]
3-5	1, 3, 4	1	100	Confidence interval [1]	5.44 [4.96,6.05]	5.61 [5.11,6.24]
3-6	1, 3, 4	1	80	Confidence interval [1]	6.14 [5.60,6.83]	6.35 [5.79,7.06]
3-7	1, 3, 4	1	1500	test Ho: 'mean change is zero' [2]	1.88 [1.71,2.09]	2.17 [1.98,2.42]
3-8	1, 3, 4	1	960	test Ho: 'mean change is zero' [2]	2.35 [2.14,2.61]	2.71 [2.48,3.02]
3-9	1, 3, 4	1	160	test Ho: 'mean change is zero' [2]	5.78 [5.27,6.42]	6.68 [6.10,7.43]
3-10	1, 3, 4	1	120	test Ho: 'mean change is zero' [2]	6.68 [6.10,7.43]	7.73 [7.05,8.60]
3-11	1, 3, 4	1	100	test Ho: 'mean change is zero' [2]	7.33 [6.69,8.16]	8.48 [7.74,9.44]
3-12	1, 3, 4	1	80	test Ho: 'mean change is zero' [2]	8.22 [7.50,9.14]	9.51 [8.67,10.58]
3-13	1, 3A, 4	2	800 + 800	test Ho: 'mean diff. is zero' [3]	3.63 [3.31,4.04]	4.20 [3.83,4.68]
3-14	1, 3A, 4	2	1500 + 100	test Ho: 'mean diff. is zero' [3]	7.56 [6.90,8.41]	8.75 [7.98,9.74]
3-15	1, 3A, 4	2	400 + 400	test Ho: 'mean diff. is zero' [3]	5.14 [4.69,5.72]	5.95 [5.43,6.62]
3-16	1, 3A, 4	2	160 + 120	test Ho: 'mean diff. is zero' [3]	8.80 [8.03,9.79]	10.19 [9.29,11.33]
3-17	1, 3A, 4	2	160 + 80	test Ho: 'mean diff. is zero' [3]	10.00 [9.12,11.13]	11.58 [10.56,12.88]
3-18	1, 3A, 4	2	80 + 80	test Ho: 'mean diff. is zero' [3]	11.55 [10.54,12.85]	13.37 [12.19,14.87]
3-19	1, 3A, 4	2	960 + 80	test Ho: 'mean diff. is zero' [3]	8.54 [7.79,9.50]	9.88 [9.01,10.99]
3-20	1, 3A, 4	2	960 + 160	test Ho: 'mean diff. is zero' [3]	6.23 [5.68,6.93]	7.21 [6.57,8.02]

[1]  $\Pr[\text{Confidence Interval's half-width will be } < X_{80}] = 0.80$

[2]  $\Pr[p < \alpha | \text{population mean change} = X_{80}] = 0.80$

[3]  $\Pr[p < \alpha | \text{population mean difference} = X_{80}] = 0.80$

[4]  $\Pr[p < \alpha | \text{population rate change} = X_{80}] = 0.80$

[5]  $\Pr[p < \alpha | \text{population rate difference} = X_{80}] = 0.80$

PRO\_measure = ADHERENCE

with Conjectures = { rate P1 = 0.80 [0.60, 0.90] }

population rates that differ by less than 0.05 will be considered equivalent

Figure	MS	Groups	N	procedure	X_80	X_90
4-1	1, 2	1	1500	Confidence interval [1]	0.02 [0.03,0.02]	0.02 [0.03,0.02]
4-2	1, 2	1	960	Confidence interval [1]	0.03 [0.03,0.02]	0.03 [0.03,0.02]
4-3	1, 2	1	160	Confidence interval [1]	0.06 [0.08,0.05]	0.07 [0.08,0.05]
4-4	1, 2	1	120	Confidence interval [1]	0.07 [0.09,0.06]	0.08 [0.09,0.06]
4-5	1, 2	1	100	Confidence interval [1]	0.08 [0.10,0.07]	0.08 [0.10,0.07]
4-6	1, 2	1	80	Confidence interval [1]	0.09 [0.11,0.07]	0.09 [0.11,0.08]
4-7	1, 2, 3A	2	800 + 800	test Ho: 'rate difference is zero' [5]	0.06 [0.07,0.05]	0.07 [0.08,0.05]
4-8	1, 2, 3A	2	800 + 800	test Ho: 'rates are equivalent(0.05)' [5]	0.00 [0.00,0.00]	0.00 [0.00,0.00]

[1] Pr[ Confidence Interval's half-width will be < X\_80 ] = 0.80

[2] Pr[ p < alpha | population mean change = X\_80 ] = 0.80

[3] Pr[ p < alpha | population mean difference = X\_80 ] = 0.80

[4] Pr[ p < alpha | population rate change = X\_80 ] = 0.80

[5] Pr[ p < alpha | population rate difference = X\_80 ] = 0.80

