#### **15.6 Overview of Plans for Manuscript #2: Medication Adherence during T1 to T2/T3**

Aim 2, Medication Adherence. The analyses concerning adherence will be based on the patient-reported Voils' Medication Adherence Survey (VMAS) at 3 months post-treatment.

Aim 2a. In the combined convenience sample of 1600 participants, two subgroups defined by mental health or substance abuse history (MH/SU Hx: yes, no) will be characterized and compared in terms of medication adherence using the VMAS. We anticipate 50% (n=800) of participants having a MH/SU Hx and 50% (n=800) without a MU/SU Hx. We hypothesize that the two subpopulations are equivalent with regard to medication adherence (<5% difference in medication adherence). Each participant's level of adherence will be classified as high (100% adherent) or low (<100% adherent) for purposes of the analysis. Overall, we anticipate that about 75% of participants will report perfect 100% adherence. Individual adherence may vary depending on treatment regimen, pill burden and patient characteristics. The adherence literature suggests that adherence decreases as the number of pills in the regimen increases (Claxton). The primary characterization of each subgroup, and their comparison, we rely on a logistic regression model for adherence conditional on *subgroup, pill burden, cirrhosis status, age, race, and sex at birth*. The analysis will focus on point estimates and confidence intervals. In particular, the rate (P) of high adherence for each subgroup, and the magnitude of difference between those two rates, are of greatest interest. Of less interest, an equivalence test procedure will be used to test the null hypothesis that the subpopulations do not have equivalent rates. 'Equivalent' will be defined to mean that the difference between population rates, ( $P_1 - P_2$ ), is less than 5%, and thus the null hypothesis is  $|P_1 - P_2| > 5\%$ . For purposes of generating new hypotheses, variations on the model will be explored using additional or alternative covariates such as *marital status, educational status, income level, living situation, employment status, health coverage*, and selected two-way interactions thereof.

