**Table 6. Anticipated Sample Sizes that May be Observed**

	Treatment Regimen	Potential Subsample*	Potential Subsample*	Combined
Genotype 1	Harvoni® (H)	480	480	960
	Zepatier® (Z)	80	80	160
	VPK®	40	40	80
Genotype 2 & 3	Daclatasvir/sofosbuvir	40	40	80
	**Sofosbuvir/velpatasvir	60	60	120
	Combined	800	800	1600

Note: \* Potential subsamples within treatment regimens may include patients with and without cirrhosis or patients with and without a mental health or substance abuse history. \*\* SOF/VEL is pan-genotypic and may also be used with Geno 1. Anticipated FDA-approval June 28, 2016. \*\*\*Participants with rare genotypes (4, 5, 6) are expected to represent <3% of the sample and will be analyzed based on prescribed treatment regimen, not genotype.

The primary objective of the study will focus on characterizing each treatment regimen or a subgroup of interest. For this purpose, point and interval estimates of mean changes from baseline for the PRO variables of interest will be estimated as a function of subgroups defined by cirrhosis status and other characteristics.

Auxiliary analyses to conduct head to head comparisons of treatment regimens is not the purpose of this study; however, we will take the opportunity to examine similarities and differences between regimens using causal inference methods.

Population inferences will rely on point and interval estimates, and secondarily on two kinds of tests: a 2-sided superiority test of the null hypothesis  $H_0$ : “the difference is exactly zero”, and an equivalence test of the null hypothesis  $H_0$ : “the magnitude of the difference exceeds a threshold that defined ‘equivalence’.”

Equivalence tests will be used for those analyses in which there is an *a priori* belief that equivalence is plausible; for example, in manuscript #2, it is conjectured that the subgroups of interest (patients with and without mental health/substance abuse histories) may be equivalent in regard to medication adherence.

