#### Anticipated level of power of equivalence tests for adherence rates

The anticipated power level of a test of equality between two subgroups each of size  $N=800$  is  $>90\%$  if the subgroup difference is  $\Delta=0.0$ . If the magnitude of difference between subgroups is larger than 0.0, then the power level is smaller.

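### Appendix row 4-8 states the null of the adherence equivalence test backwards, and its 0.00 entries and the power above 90% in 15.12 hold only near an adherence rate of 0.90

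*Combined protocol and SAP*

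**What the plan says.** Section 15.6, Aim 2a, says that "an equivalence test procedure will be used to test the null hypothesis that the subpopulations do not have equivalent rates". It puts the margin at 5% and writes the null as an absolute difference between P1 and P2 above 5%. It expects about 75% of participants to report perfect adherence and about 800 in each history group.

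Section 15.12, in the text after Table 6, gives equivalence tests in general the same direction: the null is that "the magnitude of the difference exceeds a threshold that defined" equivalence. It names manuscript #2 adherence as the example of where such a test applies.

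Later in 15.12, under the heading "Anticipated level of power of equivalence tests for adherence rates", the text reads "The anticipated power level of a test of equality between two subgroups each of size" 800 and puts the power above 90% when the difference is 0.0. It adds: "If the magnitude of difference between subgroups is larger than 0.0, then the power level is smaller".

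The ADHERENCE block of the appendix (part 2, Tabular Summary) conjectures a rate of 0.80 with range 0.60 to 0.90. It has two rows for 800 + 800. Row 4-7 is "test Ho: 'rate difference is zero' [5"]. Row 4-8 is "test Ho: 'rates are equivalent(0.05)' [5"], with X_80 and X_90 both 0.00 [0.00, 0.00]. Footnote [5] defines X_80 as the population rate difference at which the probability of p < alpha is 0.80. The column X_90 is read the same way, at 0.90.

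**The concern.** In an equivalence test the claim of interest is reached by rejecting non-equivalence, and alpha then limits the risk of declaring equivalence wrongly. Row 4-8 names equivalence itself as the null, so the row that sizes the test describes a different hypothesis from the one 15.6 will test. The wording in the 15.12 power paragraph, a test of equality, adds to the confusion, because the zero-difference test already has its own row (4-7).

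The label also makes the row's entries impossible as defined, so a reader cannot tell from the row what was calculated. The stated power then needs checking under the null that the plan intends. If it does not hold there, the plan promises a near-certain equivalence conclusion, when the groups truly do not differ, that the sample size may not deliver.

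**Working it through.** **Inputs.** n = 800 per group (15.6; appendix row 4-8). Margin 0.05 (15.6; appendix). Adherence rate P = 0.80, range 0.60 to 0.90 (appendix), and 0.75 (15.6). Test size 0.05 (15.12). The plan does not say how alpha is applied in the equivalence test; two one-sided tests at 0.05 each are assumed, without covariate adjustment or missing data.

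**1. Row 4-7 reproduces.** This is the ordinary test of zero difference. From P = 0.80, a drop of 0.06 gives 81.4% power and a drop of 0.07 gives 91.1%. These match the row's X_80 = 0.06 and X_90 = 0.07.

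**2. Row 4-8 under its own label.** If the null is that the rates are equivalent, a true difference of 0 lies inside the null and p < 0.05 occurs with probability at most 0.05. Exact enumeration of the two binomials at P = 0.80 gives a rejection probability of about 0.0%. A literal test of equality rejects about 5.0% of the time at zero difference. Neither can give 0.80 or 0.90 there.

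**3. Row 4-8 under the null of 15.6.** At zero difference:

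- SE = √(2P(1 − P)/800)
- Power = 2Φ(0.05/SE − 1.645) − 1

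| P | SE | 0.05/SE − 1.645 | Φ | Power at difference 0 |
|---|---|---|---|---|
| 0.60 | 0.0245 | 0.396 | 0.654 | 30.8% |
| 0.75 | 0.0217 | 0.664 | 0.747 | 49.4% |
| 0.80 | 0.0200 | 0.855 | 0.804 | 60.8% |
| 0.90 | 0.0150 | 1.688 | 0.954 | 90.9% |

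Exact enumeration agrees: 30.2%, 49.5%, 60.9% and 90.8%.

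**4. What row 4-8 should then show.** At P = 0.60, 0.75 and 0.80 the maximum power is below 80%, so no X_80 or X_90 exists. At P = 0.90, X_80 is 0.011 and X_90 is 0.003. To two decimals that is 0.01 and 0.00, so even there the printed X_80 is slightly off.

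**5. Sensitivity to the assumed alpha.** At P = 0.80 and zero difference:

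| Rule | Power |
|---|---|
| Two one-sided tests at 0.025 each | 41.1% |
| Two one-sided tests at 0.05 each | 60.8% |
| Two one-sided tests at 0.10 each | 77.7% |
| One one-sided test at 0.05 | 80.4% |

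None exceeds 90%.

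**6. Scale of the shortfall.** For 90% power at zero difference, n per group = 2P(1 − P)(1.645 + 1.645)²/0.05². This gives about 1,386 at P = 0.80, 1,624 at P = 0.75 and 780 at P = 0.90, against 800 planned.

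**The case against.** The strongest reply is that these are slips of wording. Section 15.6 governs the analysis and states the null correctly, in words and as an inequality. The appendix describes sample size performance, not the analysis. Its ADHERENCE block repeats the 0.05 definition of equivalence, and Figure 4-8 is titled as an equivalence figure. The 15.12 power paragraph sits under an equivalence heading, and its power is highest at zero difference and falls from there, which is how a test with a non-equivalence null behaves. The test itself is secondary: 15.6 focuses on point estimates and confidence intervals and calls the equivalence test of less interest.

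All of this stands, and it limits the point. A reader might infer that the plan holds competing hypotheses, with 15.12 using an equality null against the null of 15.6. The documents do not support that. Section 15.12 itself states the non-equivalence null and gives adherence as its example, and the power paragraph states no null at all. A reader might also infer that failing to reject would be taken as equivalence, with a high rate of false equivalence claims. No section proposes that rule, so error rates built on it describe a procedure the plan does not have. Nor can it be said that the row was calculated under the reversed null: the curve in Figure 4-8 is not available to check.

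The reply does not rescue the figures. Reading row 4-8 and the power paragraph as the intended equivalence test makes them coherent in kind, but at the plan's central and expected adherence rates the numbers are still not reproduced.

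**Conclusion.** The point holds in a limited form. Row 4-8 states the null the wrong way round against 15.6 and 15.12, and one sentence in 15.12 names the test loosely. Those two labels alone would be close to clerical. What gives the point weight is that correcting the label does not restore the numbers: power at zero difference is about 61% at the appendix's central rate of 0.80 and about 49% at the 75% expected in 15.6, against a stated figure above 90%. That figure is met only near a rate of 0.90.

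The result rests on 800 per group with complete adherence data, no covariate adjustment, and two one-sided tests at 0.05 each. The conclusion at 0.80 is the same for every alpha rule tried. At 0.90 it depends on the rule: with 0.025 per side, power there is 83.0%. The consequence is confined to a secondary test; the estimates and intervals that 15.6 puts first are unaffected.

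**What to change.** - Relabel appendix row 4-8 so that the null is |P1 − P2| ≥ 0.05.
- In the 15.12 power paragraph, replace test of equality with equivalence test.
- Regenerate row 4-8 and Figure 4-8 under that null. Where 80% or 90% power is not reached at any difference, say so instead of printing 0.00.
- Restate the power in 15.12 with the adherence rate and alpha rule it assumes, including the 75% expected in 15.6.
- Optionally, state in 15.6 that equivalence is concluded only if the 90% confidence interval for P1 − P2 lies within (−0.05, 0.05), which corresponds to two one-sided tests at 0.05 each.

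The cost is wording in two places (three with the optional rule) and one rerun of an existing calculation. Enrolment and data collection do not change. The downside is that the plan will show a less favourable power for this secondary test.
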